## DATA AND SAFETY MONITORING PLAN

2

## 3 DATA AND SAFETY MONITORING PLAN

4

a) Medical Supervision and Subject Surveillance. [name], board certified
internist and infectious diseases/HIV specialists, will serve as the Physicians of Record for the
study and has extensive experience with clinical oversight of such trials. [name] will make
final decisions regarding subject screening/enrollment and monitor/oversee clinical status and
subject safety. All of the screening data and information collected throughout the study will be
evaluated by [name].

11 b) Data Safety Monitoring Plan. To ensure the safety of subjects, they will need to meet 12 rigorous inclusion/ exclusion criteria, including comprehensive health screening procedures. The participants' personal physicians will also be informed of their patients' participation in the study. 13 14 Supervising Physician. The local investigator ([name]) will have access to all data related to 15 safety assessments. Safety will be monitored via questionnaire. Safety assessments will be performed at study visits. At the screening visit, after review of eligibility, subjects will provide a 16 17 detailed clinical history (including smoking, alcohol and medication history). Subjects will then 18 undergo a full clinical systems review.

19

The local investigator ([name]) will be available to provide direct evaluation of any clinicallyrelated concerns that might arise during the study. The principal investigator ([name]) will directly discuss with the members of UCLA IRB any concerns for adverse events and make recommendations for continuing or stopping the study. Given published safety data of Mito-MES we do not anticipate any major clinical side effects related to safety of Mito-MES especially since every effort will be made to minimize any potential side effects such as nausea

1	(administration of <80 mg of Mito-MES, administration with a full stomach, exclusion of
2	participants with known gastrointestinal disease that may predispose them to nausea).

- 3
- 4

## 5 Interpretation of Results/Statistical Analyses:

6

There is no formal hypothesis testing in this exploratory study and a comparison with a 7 8 dedicated control group. Observational and descriptive data related to efficacy and safety of use 9 of MitoQ for viral infections will be obtained and these data will set the foundation for larger 10 controlled clinical trials. All categorical and continuous data (outlined above) will be recorded as 11 median and interguartile range (given small sample size). Exploratory analyses will be 12 conducted by parametric or non-parametric tests for continuous or categorical parameters as appropriate to explore whether the primary outcomes defer between men and women. The 13 14 severity of symptoms will be compared first by categorical analysis (symptoms present yes or 15 no) via Fisher's exact Chi square, and subsequently via the independent two-sample t test for symptom severity among those who are symptomatic. Non-normally distributed data will be 16 17 analyzed via the Mann–Whitney U test. Females may have differences in mitochondria 18 compared to males of identical age. We will conduct secondary analyses to explore if effects of 19 MitoQ will vary by sex and race; however, a fully powered, sex- and race-stratified analysis is beyond the scope of this study. 20

21

Sensitivity analyses: Sensitivity analyses will be performed based on established guidelines
 regarding the performance of sensitivity analyses in clinical trials. Intention-to-treat analysis
 (as primary analysis), As-treated analysis, Per-protocol analysis will be performed to assess
 non-compliance or protocol violation. Analyses will be performed with and without outliers as

assessed by z-score or boxplot. The primary analysis will be compared with the analysis that
ignores clustering with one primary method chosen to account for clustering. Analysis will be
performed with and without adjustment for baseline characteristics. Finally, analyses will be
performed under different distributional assumptions, if applicable.

5

Adjustments for multiple comparisons: Notably, the proposed study is exploratory and there is
 less need for a multiple-testing correction, as any false-positive findings will not change practice.
 Any findings will be tested in further confirmatory clinical trials.

9

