18	[name]
19	
20	For qualifications see attached curriculum vitae
21	
22	Name and address of the research facilities to be used
23	
24	[name], PhD, Msc University of California, Los Angeles

1	Med-Infec Dis
2	[name]
3	
4	Name and address of reviewing Institutional Review Board
5	
6	UCLA OHRP https://ohrpp.research.ucla.edu/
7	[name]
8	
9	3.4. Phase of Development
10	Phase I/II efficacy and safety trial
11	
12	3.5. Objectives:
13	
14	We propose the use of Mito-MES as drug (FDA IND status) as a novel therapy for viral
15	infections including RSV and SARS-CoV-2. Our proposed use of Mito-MES can be readily
16	advanced to the clinic. In this project, we will focus on the design of an open label phase I/II
17	efficacy study to test the safety and efficacy of Mito-MES to prevent the development and
18	progression of viral infections including RSV and SARS-CoV-2 after high-risk exposure to a
19	person with suspected viral infection (post exposure prophylaxis study). We focus on post
20	exposure prophylaxis study in adults (see study design) and not acute treatment study, since a
21	post exposure prophylaxis study design may require a much smaller sample size to show
22	efficacy and may be more feasible with current resources compared to an acute treatment

24

23

study.

1 Primary objectives:

2

• To determine the efficacy of the treatment with mito-MES 20 mg daily for up to 14 days to prevent development of any viral infection (Yes/no) in high-risk close household contacts of cases with viral infection

To determine the efficacy of the treatment with mito-MES 20 mg daily for up to 14 days to
 prevent development of severe clinical symptoms of any viral infection in high-risk close
 household contacts of cases with viral infection.

9

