9 on history and the study definition in the household within 5 days prior to study entry. Highrisk exposure was defined as prolonged (>24 hour) and intimate (< 6 feet) exposure to index 10 case without personal protective equipment (e.g., face mask) in poorly ventilated indoor 11 12 areas. To increase chances that differences in treatment efficacy between the compared 13 groups will be shown will as small sample size as possible, the study team enrolled participants with particularly high risk exposure to the index case defined as: a) direct care 14 for the index case; b) had close direct physical contact with the index case; c) lived with the 15 index case; d) had close indoor contact (within 6 feet), with or without direct physical 16 17 contact, for at least 24 hours; e) had direct contact with infectious body fluids, including oral secretions, respiratory secretions, or stool. For example, we included several parents that 18 were exposed to infected children (who also infected their siblings) and included an 19 extended window of recurrent and continuous high-risk exposure to independent confirmed 20 21 SARS-CoV-2 infections within the household. In these particularly high-risk exposures, there was direct contact with children during childcare and while the children were symptomatic 22 (fever, cough, coryza, fatigue); 23

5. With at least 4 COVID-19 diagnostic tests in case of negative test results. To minimize
 false negative tests, we included participants who had multiple independent SARS-CoV-2
 diagnostic tests with sensitivity >90% per test;

Adequate renal function determined by the Cockcroft-Gault formula for creatinine clearance
 (>60 mL/min/1.73 m2

3 7. Able and willing to communicate in English

4 8. Able and willing to provide informed consent to take part in the study

5 9. Able and willing to provide medical/surgical history

6 10. Availability to have follow up for all study visits, barring unforeseen circumstances

- 7
- 8

In addition, for the *mito-MES group*, the following inclusion criteria were applied:

9

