1. Initiation of Mito-MES within 5 days since exposure to index case. To ensure that a study 10 participant met this inclusion criterion, the study participant should have had high-risk close 11 12 contact with a confirmed COVID-19 case within the past 1-4 days prior to study entry. This 13 4-day window would also allow for up to 24-hour period for initiation of intervention (mito-MES) so that mito-MES would be started within 5 days since exposure to index case; 14 2. Successfully contacted by the study team within 24 h of study team notification of the 15 16 relevant index COVID-19 case. This time window is necessary because the efficacy of PEP 17 may be dependent on the timing of its initiation. Every effort was made by the study team to 18 include study participants who would be able to initiate mito-MES as soon as possible after notification of exposure to index case of SARS-CoV-2 infection. For many study participants, 19 Mito-MES was provided immediately after informed consent so that it would be available for 20 21 immediate use after anticipated exposure to confirmed case of SARS-CoV-2. It is well established that antivirals have highest efficacy when given as soon as possible (ideally 22 within 48 hours). This design with immediate initiation of Mito-MES within 72 hours post 23 24 exposure is different than the study design in a randomized controlled Phase 2/3 EPIC-PEP 25 (Evaluation of Protease Inhibition for COVID-19 in Post-Exposure Prophylaxis) of paxlovid given within 5 days post exposure from SARS-CoV-2 that failed to demonstrate therapeutic 26

1		efficacy (unpublished data). Time of initiation of the post-exposure prophylaxis (PEP)
2		treatment is critical in the setting of emerging SARS-CoV-2 variants that may establish
3		infection in less than 5 days.
4	3.	Ineligible for FDA approved alternative treatments to prevent progression to severe viral
5		infection including COVID-19 based on established criteria
6		https://www.cdc.gov/coronavirus/2019-ncov/need-extra-precautions/people-with-medical-
7		conditions.html. Rationale: If the study participant has confirmed exposure to SARS-CoV-2,
8		the participant will be allowed to enroll only if he/she is eligible for other FDA approved
9		treatments such as monoclonal antibodies or other antivirals for reasons such as personal
10		choice, allergies or lack of availability.
11	11	Willing to follow sexual abstinence during study period or highly effective method of

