## 4 Participant timeline

5

6 Study Outline/Schedule of events/ Participant Timeline: Potential participants are screened for

7 study eligibility by telephone ± video link; consenting individuals undergo a remote (via video-

8 link or, if not feasible, by telephone) baseline visit (day 1) within 24 h. Subsequent remote visits

9 occur on days 1, 7, 14. The full schedule of events is shown in Table 4.

Timepoints (D0 is the day of	Before (<) D0	D1	D7	D14	D21
study entry)	or D0-D4				
Eligibility assessment	х				
Informed consent	X				

Dispensation of study drug (Mito	- X				
MES arm)					
Assessment by study staff		Х	X	х	х
Drug/no drug treatment					
Adherence assessment		Daily D1	-14		
Symptoms assessment		Daily D1	-14		
Temperature assessment		Daily D1	-14		
Concomitant medication					
assessment					
Self-collected Nasal swab	Х	Daily D1	-D21		
(PCR/rapid antigen test)					
Adverse event assessment			Х	Х	X

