## 6 Power/Sample Size:

7

8 The study is purely exploratory and is not powered to do a formal hypothesis testing. The data 9 from this study will set the basis for large randomized controlled clinical trials to test the safety of 10 mito-MES in the setting of treatment of viral illnesses. In addition, preliminary data will be 11 obtained on the efficacy of Mito-MES to reduce severity of viral illness. More specifically, all the proposed primary endpoints of efficacy are based on objective quantifiable criteria (fever based 12 on thermometer, duration of symptoms based on number of days, severity of viral illness based 13 14 on quantitative summary score that considers at least two independent symptoms of viral illness based on a clinically relevant definition of viral illness made by a physician). The "effect size" of 15 16 the intervention Mito-MES on these quantifiable outcomes of viral illness in humans will be 17 determined. The safety of Mito-MES in the setting of viral illness will be recorded. This is essential information for the design of larger RCT studies. 18

19

20 Based on resources, we enrolled 80 study participants.

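### The plan conflicts on whether an untreated comparator exists, defines no contrast for the drug effect it promises, and drops SARS-CoV-2-positive participants from the final analysis

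*Combined protocol and SAP*

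**What the plan says.** **Comparator.** In Interpretation of Results/Statistical Analyses, the sentence "There is no formal hypothesis testing in this exploratory study and a comparison with a" runs on to a dedicated control group. The grammar admits two readings. The next sentence calls the data observational and descriptive and looks ahead to larger controlled trials, so the natural reading is that there is no control comparison. The only groups this section names for comparing the primary outcomes are men and women. A two-group comparison of symptom presence and severity (Fisher, t, Mann–Whitney) follows without naming its groups. The Summary and the Overview of study design describe an open-label study and name no control.

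Other places presuppose an untreated group. Inclusion criterion 4 explains its choice of very high-risk exposures with the words "To increase chances that differences in treatment efficacy between the compared" groups will be shown. After the common inclusion list, "the following inclusion criteria were applied" to the mito-MES group only. These include "contact with a confirmed COVID-19 case within the past 1-4 days prior to study entry", successful contact by the team within 24 hours, and a condition on alternative approved treatments. The schedule of events in Participant timeline has a row labelled "Drug/no drug treatment" and refers to a mito-MES arm.

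**Promise.** Both primary objectives begin "To determine the efficacy of the treatment with mito-MES 20 mg daily for up to 14 days to" prevent infection or severe symptoms. Power/Sample Size says that the effect size of "the intervention Mito-MES on these quantifiable outcomes of viral illness in humans will be" determined. It closes with "Based on resources, we enrolled 80 study participants", without a split.

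**Analysis set.** The paragraph just before the exclusion criteria allows entry without waiting for a test result. It then leaves participants with a positive SARS-CoV-2 test during the study out of the final analysis. The Sensitivity analyses paragraph makes intention-to-treat the primary analysis. Symptomatic PCR-confirmed SARS-CoV-2 infection is a listed secondary outcome.

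**The concern.** A reader cannot tell whether 80 people or fewer took the drug, or what the promised effect would be measured against. An analyst who follows the statistical section has a contrast between men and women but none between treated and untreated. Whatever is then reported as the effect of mito-MES would be either an illness rate in treated people or a comparison of groups selected by different rules.

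The exclusion of positives is a separate fault. SARS-CoV-2 is a named target of the prophylaxis, so the rule removes people because of something that happens after entry and that is itself an outcome. The plan calls its output essential for the design of larger randomised trials, so it matters that the number means what it is said to mean.

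**Working it through.** **No figure to reproduce.** The 80 is set by resources. The documents give no attack rate, effect size, allocation ratio, household size or intra-cluster correlation. Every rate and split below is an assumption, used only to show size and direction.

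**1. The texts side by side.**
- For a comparator: inclusion criterion 4 (compared groups) and the criteria for the mito-MES group only. The schedule of events is weaker support.
- Against: the Summary, the Overview of study design, and the natural reading of the statistical section.
- Neutral: the two-group tests, which may refer only to men and women.
- Absent everywhere: source, assignment and number of untreated participants, an external benchmark, and a treated-versus-untreated contrast.

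**2. If all 80 were treated.** Assume 12/80 ill, which is 15% (exact 95% CI 8.0% to 24.7%). The apparent risk ratio is 0.15/c, where c is the unknown untreated rate:
- c = 10%: 1.50
- c = 20%: 0.75
- c = 30%: 0.50
- c = 40%: 0.375

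The same data fit harm or benefit, depending on a number the plan does not supply. Household clustering widens the interval. The design effect is 1 + (m − 1) × ICC. With m = 2 and ICC 0.2 it is 1.2, and with m = 3 and ICC 0.4 it is 1.8. The effective sample is 80/1.2 = 66.7 or 80/1.8 = 44.4, and the interval becomes 7.4% to 25.9% or 6.1% to 28.9%.

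**3. If some of the 80 were untreated.** Everyone needs high-risk exposure to a suspected case. Only the mito-MES group also needs recent contact with a confirmed COVID-19 case, team contact within 24 hours, and a given alternative-treatment status. The Treatments section then accepts an unconfirmed index infection, which conflicts with the confirmed-case criterion. A treated-versus-untreated contrast can be computed, but the groups differ by construction and no assignment rule is stated.

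**4. Removing SARS-CoV-2 positives.** Start from the assumed 12/80.
- If k of the 12 ill are positive and removed, the rate is (12 − k)/(80 − k). For k = 3 it is 9/77 = 11.7%, for k = 6 it is 6/74 = 8.1%, and for k = 9 it is 3/71 = 4.2%.
- If instead 6 symptom-free positives are removed, the rate rises to 12/74 = 16.2%.
- With two groups, an inert drug and equal proportions removed from each, the risk ratio stays at 1.00.
- With an assumed 6/40 versus 12/40 (risk ratio 0.50), remove 25%, 50% or 75% of the ill in each group. The ratios are (4.5/38.5)/(9/37) = 0.48, (3/37)/(6/34) = 0.46 and (1.5/35.5)/(3/31) = 0.44. The fractional counts are expected values.

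Whatever the numbers, the outcome of symptomatic PCR-confirmed SARS-CoV-2 infection has no events left if the rule is applied.

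**5. Time origin.** The primary outcome runs for 14 days from exposure. Participants must be symptom-free at entry, and entry may come up to 5 days after exposure. Up to 5 of the 14 days are therefore event-free by design. If entry delay differs between groups, counting from exposure favours the group that enters later. The day-0 definitions also conflict: it is study entry in Participant timeline and exposure in Sessions by study staff.

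**The case against.** The strongest reply is that most of this is disclosed. The plan calls itself purely exploratory, disclaims formal testing, describes its data as observational and descriptive, and says findings will be retested. That answers any complaint about imprecision. It does not answer an undefined contrast, because an exploratory estimate still needs something to be an estimate of.

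The exclusion of positives also has a context. It follows permission to enter before a test result is known, and a swab is scheduled at or before entry, so some removed participants may already have been infected at entry. That stands as a reason for a sensitivity analysis. The rule, however, speaks of a positive test during the study and is not limited to infection at entry.

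Three stronger readings are tempting, and the documents support none of them:
- A reader might infer that the exclusion makes an inert drug look effective whichever design is meant. Dividing 11.7%, 8.1% and 4.2% by 15% does give 0.78, 0.54 and 0.28. Those ratios need an external untreated rate of 15% that counts SARS-CoV-2 illness, and the plan proposes no external rate.
- A reader might infer that 80 participants are too few. Powering is openly disclaimed, so this is not an error.
- A reader might infer that later trials will be sized on the reported effect. The plan says only that the information is essential to their design.

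A remedy must also be modest. Several baseline factors collected at screening (kidney, liver and heart disease) are largely excluded at entry, and exposure intensity is not among those listed. The assumed 6 + 12 = 18 events could not carry broad adjustment plus clustering.

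**Conclusion.** The point holds and needs correction before any drug effect is reported. The documents contradict themselves on the existence of an untreated group, and they promise efficacy and an effect size without a contrast or benchmark. Without an untreated group the drug effect is not identified. With one, only a non-randomised association between differently selected groups is available. These conclusions rest on the text, not on a calculation.

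The exclusion of positives contradicts the intention-to-treat primary analysis and empties a listed outcome; that also follows from the text alone. It removes symptomatic target events from the primary outcome as well. How far this moves the estimate, and in which direction, depends on assumptions the documents do not settle: who tests positive, whether they have symptoms, and whether there are two groups.

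**What to change.** **Analysis set.** Keep all enrolled participants in the primary intention-to-treat analysis whatever their SARS-CoV-2 result, including those who leave study treatment. Count symptomatic positives as primary events. Keep symptom-free positives in the denominator and count them as confirmed infections. Add a sensitivity analysis without those whose swab at or before entry was positive.

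**Comparator.** State whether a no-drug group exists. Reconcile inclusion criterion 4, the mito-MES-only criteria, the Treatments section, the schedule of events and the statistical section accordingly.

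- *If none exists:* remove the comparator wording. Restate the primary objectives and the effect-size sentence as incidence and severity of viral illness in treated contacts, with 95% confidence intervals that allow for household clustering. Describe sex and race results as outcome differences among treated participants, not as differences in drug effect.
- *If one exists:* give its size and how its members were assigned. Name the treated-versus-untreated contrast. Restrict the comparison to eligibility criteria that can apply to both groups. Reconcile day 0, and either start follow-up at study entry with time since exposure as a covariate or use delayed-entry methods. Adjust for only a few baseline factors and for household clustering. Report the result as a non-randomised association.

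Because 80 participants are described as already enrolled, label all of these changes as post hoc.

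**Cost.** Changes of wording, one analysis-set rule, one sensitivity analysis and at most one restricted comparison, with no new arm and no further participants. The price is weaker claims, wider intervals and possibly fewer participants in the restricted comparison.

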1 diagnostic test such as SARS-CoV-2 FDA approved test (can delay initiation of treatment for at 2 least 24-48 hours). If a participant has a positive SARS-CoV-2 during the study, then the participant will be allowed to continue the study only if not eligible for another FDA approved 3 treatment for COVID-19, given the potential favorable antiviral and anti-inflammatory effects of 4 5 mito-MES in SARS-CoV-2 infection. However, these participants with a positive SARS-CoV-2 6 test will not be included in the final analysis of this PEP trial. The data obtained from the participants with a positive SARS-CoV-2 test will set the foundation for future studies of use of 7 8 mito-MES as treatment for acute COVID-19. 9 Exclusion criteria for all study participants: 10 11 Participants who meet any of the following criteria at screening will be excluded from the study: 12 1. Use of Coenzyme Q10 or Vitamin E < 120 days from enrollment 13 2. Women with variations in physiological functions due to hormones that may effect immune 14 function and (transgender, **pregnant**, breastfeeding) 3. Pregnant (based on history) or lactating. If the possible study participant is female and 15 sexually active and there is a possibility based on history (timing of most recent sexual 16 17 intercourse and timing of menstrual period) that the possible study participant is pregnant, then the participant will be excluded from the study. Rationale: Additional pregnancy testing 18 will further delay the initiation of treatment and will further compromise feasibility of the study 19

20 given limited resources.

Absence of significant clinical disease clinical diseases [e.g., cardiovascular disease (such as coronary artery/vascular disease, stroke), heart disease (such as congestive heart failure, cardiomyopathy, atrial fibrillation), lung disease (such as chronic obstructive pulmonary disease, asthma, bronchiectasis, pulmonary fibrosis, pleural effusions), kidney disease (glomerular filtration rate or GFR less than 60 ml/min/1.73 m2), liver disease (such as

cirrhosis, hepatitis), cancer, major immunosuppression (such as history of transplantation,

1		HIV infection)] based on history. Rationale: Significant clinical diseases can confound
2		interpretation of results for safety and efficacy (e.g., symptomatic viral infection). For
3		example, a patient with known major lung disease such as chronic obstructive pulmonary

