## Main Parameters of Safety

,	•		
۰.	,		
	/		
4	1		

_	
3	Adverse events (day 7, 14): the proportion of participants exhibiting adverse events of
4	any grade as defined using the established  grading scales for the severity of adverse
5	event, such as the Toxicity Grading Scale for Healthy Adult and Adolescent Volunteers
6	Enrolled in Preventive Vaccine Clinical Trials
7	https://www.fda.gov/media/73679/download).
8	
9	Main Parameters of Efficacy
10	
11	Primary measures of efficacy (will be assessed in ALL the study participants):
12	
13	The following primary outcomes are based on criteria that can be obtained reliably and
14	consistently for all the study participants (based on history and thermometer).
15	
16	• Development of any symptom of viral infection within 14 days after exposure (YES/No).
17	• Severity of viral illness based on a quantitative score system. Each of the above 14
18	symptoms will be given a score based on severity: 1 for mild, 2 for moderate, 3 for severe.
19	Then a total severity score will be estimated (range of score is 0-42). Common example: a
20	person with mild coryza, sore throat and cough will be given a score of 3.
21	
22	
23	Secondary measures of efficacy (will be assessed in study participants but some endpoints
24	such as diagnostic tests may not be available in all the study participants):
25	

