1 The following secondary outcomes are based on **either non guantitative** criteria (categorical) 2 or criteria that may not be available for all the study participants (for example FDA approved diagnostic tests). The study will not pay for any diagnostic tests. These diagnostic tests for 3 viruses may be available in the setting of real world setting and clinical care of each participant 4 5 (for example if performed by the participant or ordered by a doctor in the setting of clinical care). 6 Development of new onset fever (T> 100.3 F or 38C) based on documented 7 8 measurements of temperature on a daily basis throughout the duration of the study. 9 Temperature will be recorded in a diary and recording temperature would be a requirement 10 for study participation. 11 **Duration** of ANY of at least three respiratory/systemic symptom of viral illness in **days** (Symptom 1: fever, Symptom 2: cough, Symptom 3: coryza, Symptom 4: sore throat, 12 Symptom 5: shortness of breath, Symptom 6: chills, Symptom 7: fatigue, Symptom 8: loss 13 of smell or taste, Symptom 9: myalgias, Symptom 10: arthralgias, Symptom 11: headache, 14 Symptom 12: nausea, Symptom 13: vomiting, Symptom 14: diarrhea 15 Confirmation of viral infection based on a FDA approved diagnostic test (for example 16 17 respiratory panel PCR that also detects RSV and influenza or other respiratory viruses, rapid antigen test for SARS-CoV-2, PCR for SARS-CoV-2). 18 Symptomatic viral infection: proportion of participants with fever, cough, or other 19 20 respiratory/systemic symptoms (including but not limited to fatigue, loss of smell or taste, 21 myalgias, arthralgias, shortness of breath, sore throat, headache, chills, coryza, nausea, 22 vomiting, diarrhea). 23 Symptomatic moderate to severe viral infection. Based on established score system a viral illness will be categorized as moderate or severe if the participant grades at least 2 different 24 25 symptoms as "moderate" or "severe".

- Symptomatic PCR confirmed SARS-CoV-2 infection
- 2 Need for oxygen therapy (days)
- Hospitalization: Days of hospitalization attributable to viral disease: The median number of
   days (or partial days) spent admitted to an acute care hospital
- Respiratory failure requiring ventilatory support attributable to viral disease: The median
   number of days (or partial days) requiring (i) non-invasive or (ii) invasive ventilation

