- Mortality (proportion of participants who die) attributable to viral disease and all-cause
   mortality
- 9
- 10 **3.12 Experimental protocol of study**
- 11

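### Yes/no outcomes are to be summarised by median and interquartile range, which hides how many fell ill and conflicts with outcomes defined as proportions; no confidence interval is planned

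*Combined protocol and SAP*

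**What the plan says.** The reporting rule is one sentence in Interpretation of Results/Statistical Analyses, split here by a line break: "All categorical and continuous data (outlined above) will be recorded as" "median and interguartile range (given small sample size".

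The outcomes it must cover include:
- First primary outcome (Main Parameters of Efficacy): "Development of any symptom of viral infection within 14 days after exposure (YES/No". No other summary measure is given for it.
- Safety (Main Parameters of Safety): "the proportion of participants exhibiting adverse events of" any grade, on days 7 and 14.
- Secondary efficacy: "Symptomatic viral infection: proportion of participants with fever, cough, or other" respiratory or systemic symptoms.
- Secondary efficacy: "Mortality (proportion of participants who die) attributable to viral disease and all-cause" mortality.

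The statistics section disclaims formal hypothesis testing. It says that data on the use "of MitoQ for viral infections will be obtained and these data will set the foundation for larger" controlled trials. Power/Sample Size adds that the size of the effect will be determined as input to later randomised trials, and it gives 80 as the number enrolled. Neither section mentions a confidence interval, and none appears elsewhere in the document. The statistics section does plan a Fisher's exact comparison of symptoms present or absent. Under Sensitivity analyses it treats a method that accounts for clustering as primary and the analysis that ignores clustering as the comparison.

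**The concern.** In a study without formal tests, the descriptive summary is the result. Someone designing a later trial on a yes/no endpoint needs two things from this one: the event rate and its precision. Read literally, the reporting rule withholds the first and nothing in the plan asks for the second.

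The same rule would govern adverse events. An event in fewer than a quarter of participants would print exactly like no events at all. Median and interquartile range suit the severity score and the day counts, and the hospitalisation and ventilation outcomes are themselves defined by medians. The fault is therefore confined to the categorical outcomes.

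**Working it through.** The plan has no calculation of its own to reproduce. It states no event rate, error rate, power or target precision, and the 80 is set by resources.

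**Inputs.** N = 80 (Power/Sample Size); outcome coded 0/1 (Main Parameters of Efficacy); summary = median with lower and upper quartile (Interpretation of Results/Statistical Analyses). Assumptions: all 80 are summarised together; where an interval is shown, it is 95% two-sided. The event rate is not given, so every possible count k = 0 to 80 was tried.

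**Step 1: what the summary prints.** Sort the values: 80 − k zeros, then k ones. Under nine standard quantile definitions the lower quartile lies between the 20th and 21st values, the median between the 40th and 41st, and the upper quartile between the 60th and 61st. The 61st value is 1 only if 80 − k ≤ 60, that is k ≥ 20; the 60th is 1 only if k ≥ 21. So the upper quartile is 0 for k ≤ 19 and 1 for k ≥ 21. The same argument puts the switch for the median at k = 40 and for the lower quartile at k = 60.

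| Number ill of 80 | Printed median (IQR) |
|---|---|
| 0-19 | 0 (0-0) |
| 21-39 | 0 (0-1) |
| 41-59 | 1 (0-1) |
| 61-80 | 1 (1-1) |
| 20, 40, 60 | depends on the quantile definition |

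Six of the nine definitions give 20, 40 and 60 a printed result of their own, so 3 of 81 counts (3/81 = 3.7%) can be read back. The other three definitions identify no count.

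**Step 2: how much is hidden.** A printed 0 (0-0) covers everything from 0/80 = 0% to 19/80 = 23.75%. Exact limits are lower = the 0.025 quantile of Beta(x, n − x + 1) and upper = the 0.975 quantile of Beta(x + 1, n − x); for x = 0 the lower limit is 0 and the upper limit is 1 − 0.025^(1/n). These treat participants as independent:
- 0/80: upper limit 1 − 0.025^(1/80) = 4.5%, so 0 to 4.5%
- 8/80 = 10%: 4.4 to 18.8%
- 16/80 = 20%: 11.9 to 30.4%
- 19/80 = 23.75%: 14.9 to 34.6%

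All four would be printed identically.

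**Step 3: does it depend on N = 80?** The analysed set may be smaller. The text before the exclusion criteria says that participants with a positive SARS-CoV-2 "test will not be included in the final analysis of this PEP trial", and inclusion criterion 4 speaks of groups being compared. With an assumed N of 60, counts 0-14 all print 0 (0-0) and at most 3 of 61 can be read back. With an assumed N of 40, counts 0-9 do so and at most 3 of 41 can be read back.

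**Step 4: consistency.** A proportion cannot in general be derived from a median and quartiles. The reporting rule therefore cannot deliver the three outcomes defined as proportions (adverse events, symptomatic viral infection, mortality).

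**The case against.** The best defence is that the sentence is loose drafting. Symptomatic viral infection is nearly the same event as the yes/no primary outcome and is already defined as a proportion, and Fisher's exact test cannot be run without counts. Much of this stands: counts will exist and the error can be repaired. A reader might infer that the event rate would be lost for good; the documents do not support that. But the sentence names categorical data expressly, and a test comparing groups neither requires a rate to be reported nor gives an interval for it.

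A second defence is that the study is exploratory, that a reader can derive a simple interval from n/N, and that the planned mixed models and clustering method would ordinarily yield standard errors. The plan does not commit to reporting either n/N or those standard errors. A simple interval also ignores clustering, which the plan's own primary method does not.

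Three further readings are tempting and go too far:
- *That the primary outcome's own definition contradicts the rule.* It does not. The proportions belong to the safety outcome and two secondary outcomes; the primary outcome simply has no other summary.
- *That the sensitivity run with and without outliers would remove every ill participant.* The text does not say that this run covers yes/no data. It also allows a z-score as well as a boxplot, and an assumed cut-off of |z| > 3 would flag ill participants only at 1-7 of 80.
- *That the counts printed alike are always statistically distinguishable.* The intervals for 0/80 and 19/80 are disjoint only if participants are independent, and these are household contacts. At an assumed N of 40, an assumed design effect of 1.25 makes the intervals for 0/40 and 9/40 overlap (0 to 10.9% and 9.7 to 40.7%). The point does not need this claim.

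**Conclusion.** The point holds. As written, the reporting rule gives an uninformative summary of a primary outcome: 0 to 19 ill of 80 look the same, and at most 3 of 81 counts can be recovered. It conflicts with three outcomes defined as proportions, and no confidence interval is planned for any outcome, although the stated purpose is to inform larger trials.

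The figures assume that all 80 are summarised together; the pattern is the same at assumed sizes of 60 and 40. The consequence is limited because the counts needed for a proper report will be available. This is a reporting contradiction and an omission of precision. It is not a loss of data and does not invalidate the study.

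**What to change.** Replace the sentence in Interpretation of Results/Statistical Analyses with wording to this effect:
- Binary and other categorical outcomes, including adverse events, are reported as n/N (%), with N the number in the analysed set.
- Each binary outcome has a 95% confidence interval that allows for household clustering, in line with the plan's primary method. The simple exact (Clopper-Pearson) interval serves as the analysis that ignores clustering, or applies where each household contributes one participant.
- Median (IQR) is kept for the severity score, day counts and continuous data.

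The cost is a slightly larger table and a little more analysis work. No data are needed beyond what the planned clustering analysis already requires, which includes a household identifier.
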